### ***3.4 Study Drug preparation and administration***

#### **Octreotide (Sandostatin® 100 $\mu$ g/ml, Novartis Ireland)**

- The drug will be stored in line with manufacturer instructions.
- As the study drug will be blinded to the research investigator, the research nurse will be charged with preparing the study drug.
- A dose of 1 $\mu$ g/Kg will be drawn up by the research nurse and labeled with the appropriate code **Treatment A** or **Treatment B**.

- The weight used will have been recorded prior to drug administration
- This drug will be administered using a sterile technique to the participant's subcutaneous tissue.
- It will be given 60 minutes prior to the Buffet meal.
- A menstrual history and urinary pregnancy test will be completed on all females of child bearing potential prior to the administration of any drug.

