### ***3.2.6 Urinary pregnancy test***

Urine specimens will be collected on all women with child bearing potential prior to the administration of any drugs which the investigator and participant are blinded to. A spot urine sample will be collected from participants, transferred to the biochemistry lab and analysed for  $\beta$ HCG according to standardised method in the laboratory. Samples will be labelled with the volunteers name, date of birth and medical record number where available. Volunteers with an unexpected positive pregnancy will be informed by the investigator of the result, excluded from the study and referred to their primary care physician for further assessment.

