##### **Study Visit 3: Week 52**

1. Anthropometric Assessment: Height, weight, BMI and waist circumference
2. Fasting Gut peptide level
3. Randomisation to treatment A or B (Saline or Octreotide)
4. Administration of blinded Study drug prior to buffet meal
5. Buffet meal
6. Post prandial bloods
7. Urinary Pregnancy test

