##### **Study Visit 4: Week 52**

1. Anthropometric Assessment: Height, weight, BMI and waist circumference
2. Fasting Gut peptide level

3. Administration of blinded study drug prior to buffet meal(A or B determined by previous randomization)
4. Buffet meal
5. Post prandial bloods
6. Urinary Pregnancy test

### Study Visit 5: Week 102

1. Anthropometric Assessment: Height, weight, BMI and waist circumference
2. Fasting Bloods
3. Buffet meal
4. Post Prandial Bloods
5. Discharge from study/Letter to General Practitioner

	Screening Visit	Visit 1 Week -4	Visit 2 Week 12	Visit 3 Week 52	Visit 4 Week 52	Visit 5 Week 104
Informed Consent	X	X				
Height		X	X	X	X	
Weight		X	X	X	X	
Fat mass		X	X		X	
Blood pressure		X	X	X	X	X
Heart rate		X	X	X	X	X
Medical History		X				X
Fasting Gut Peptides		X	X	X	X	X
Post Prandial Gut Peptides		X	X	X	X	X
Pregnancy test		X	X	X	X	X
Administration of Study Drug				X	X	
Food preference Questionnaire	X					
Buffet meal			X		X	
Clinical Nutrition session		X				
GP letter	X					X

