**TABLE 3: General study visit schedule**

Time	Action
10:30 to 12.00	Arrive at CRC Complete paperwork, questionnaires and collection of anthropometric data
10.50	Phlebotomy 1 (fasting pre-meal)
11.00	SC injection of octreotide or saline as randomised at 52 week visit
12.00	Commence ad libitum buffet meal Upon completion of the ad libitum meal
14.00	Phlebotomy 2 at 2 hours post meal initiation
14.15	End of Visit

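### The pregnancy test must precede any drug, but the Visit 3 and 4 lists place it last and Table 3 gives it no slot before the 11:00 injection

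*Combined protocol and SAP*

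**What the plan says.** Four parts of the combined protocol and SAP bear on this.

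- **Section 3.4 (drug preparation and administration).** The same sentence appears under octreotide and under the saline placebo: "A menstrual history and urinary pregnancy test will be completed on all females of child bearing potential prior to the administration of any drug".
- **Section 3.2.6 (urinary pregnancy test).** "Urine specimens will be collected on all women with child bearing potential prior to the administration of any drugs" to which investigator and participant are blinded. The sample is then "transferred to the biochemistry lab and analysed for" βHCG. A woman with an unexpected positive result is told, excluded and referred to her primary care physician. Pregnancy is also an exclusion criterion in section 3.1.2.
- **Section 4, visit lists.** At Visit 3, item 4 is "Administration of blinded Study drug prior to buffet meal" and item 7, the last, is "Urinary Pregnancy test". At Visit 4, item 3 is "Administration of blinded study drug prior to buffet meal(A or B determined by previous randomization" and the pregnancy test is again last, at item 6.
- **Section 4, Tables 2 and 3.** Table 2 marks a pregnancy test at Visits 3 and 4 but gives no order within a visit. Table 3 puts "SC injection of octreotide or saline as randomised at 52 week visit" at 11:00 and "Phlebotomy 2 at 2 hours post meal initiation" at 14:00. It has no line for a pregnancy test.

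**The concern.** The rule and the schedule disagree on a safety step. Section 3.4 makes the test a condition of dosing, while the section that staff would use to run the visit lists it after dosing.

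There are two ways this could go wrong. Someone working down a visit list, or from Table 3, gets no prompt to make the check before the injection. Someone working from section 3.2.6 could collect the urine, send it to the laboratory and inject with the result outstanding. In either case a pregnant participant could receive octreotide before the test that should exclude her is read.

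There is a lesser consequence at Visit 3. Randomisation is listed before the test, so a woman could be randomised and then have to be excluded.

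**Working it through.** The plan states no figure to reproduce, so the check sets the rule beside each part of the schedule.

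**Order in the visit lists (section 4)**

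| Step | Visit 3 item | Visit 4 item |
|---|---|---|
| Anthropometry | 1 | 1 |
| Fasting gut peptides | 2 | 2 |
| Randomisation | 3 | not applicable |
| Study drug | 4 | 3 |
| Buffet meal | 5 | 4 |
| Post-prandial bloods | 6 | 5 |
| Pregnancy test | 7 (last) | 6 (last) |

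Distance from drug to test: 7 − 4 = 3 items at Visit 3, and 6 − 3 = 3 items at Visit 4.

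Every other item follows the order of the day. The other pre-dose condition in section 3.4, that weight be recorded before the drug, is met at item 1. Only the pregnancy test is out of sequence.

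**Times in Table 3**

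- Before the injection: arrival at 10:30 with paperwork, questionnaires and anthropometry, then fasting phlebotomy at 10:50.
- Injection: 11:00.
- Lines before 11:00 that name urine collection, menstrual history or a test result: 0.
- If the test is done where the lists put it, after the 14:00 sample, the delay from the injection is at least 14:00 − 11:00 = 3 hours.

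**Menstrual history.** It is named only in section 3.4 (under both products). It appears in neither drug-visit list, nor in Table 2 or Table 3. The medical history row of Table 2 is marked at Visits 1 and 5 only, so it does not cover the drug visits.

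**Section 3.2.6 against section 3.4.** Section 3.4 requires the test to be complete before dosing. Section 3.2.6 requires the specimen to be collected before dosing and sends it to a laboratory. It says what follows a positive result but not that the result must be known before the injection. Nothing in the document makes dosing wait for a documented negative result.

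**What cannot be checked.** Table 3 leaves 30 minutes between arrival (10:30) and injection (11:00). The document gives no laboratory turnaround time, so it cannot be said whether that is enough.

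**The case against.** The strongest reply is that section 3.4 is explicit, appears under both products, and sits in the instructions that the nurse preparing the drug must follow. On a fair reading it governs. Sections 3.2.6 and 3.4 are also compatible: collect before the drug, and complete before the drug. The plan does not tell anyone to dose first. This stands, and it limits the point to a risk of error at the site.

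Next, the lists are not declared chronological, and section 4 describes Table 3 as only a basic outline of a typical visit. Table 3 also omits randomisation, drug preparation, blood pressure and heart rate. So its missing line is an omission, not an instruction to test later. That stands too. It does not dispose of the lists, which otherwise run in time order within an overview that section 4 calls detailed. And since Table 3 does include the 52-week injection, the check that must precede it belongs there.

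It can also be said that staff are prompted to test, because both lists and Table 2 name the test. That is so; what is missing is a prompt to do it before the injection.

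Three points of scope are fair. Only participants eligible for randomisation are injected, so the women at risk are those of child-bearing potential who actually receive study drug. The 3-hour figure applies only if staff follow the list order against section 3.4. And testing before randomisation is a recommendation: the plan requires the test before drug, not before randomisation.

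**Conclusion.** The concern holds, and the schedule is wrong as written: the listed order at both drug visits contradicts the stated rule, and following it would dose women before an exclusion criterion is checked. It should be corrected.

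The size is two visits, for each woman of child-bearing potential who is randomised and injected. The document gives neither the number of such women nor the risk to a pregnancy from a single 1 µg/kg dose, so neither is estimated here.

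The conclusion rests on reading the visit lists as time-ordered, which their other items support. It assumes nothing about laboratory turnaround. This is a matter of participant safety and internal consistency, with no bearing on power or type I error.

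**What to change.** 1. In the Visit 3 list, move the pregnancy test ahead of randomisation and add the menstrual history beside it.
2. In the Visit 4 list, place both ahead of drug administration.
3. In Table 3, add a line before 11:00 for menstrual history, urine collection and result at the 52-week visits.
4. In sections 3.2.6 and 3.4, add a sentence that a documented negative result must be seen before the injection for every woman of child-bearing potential.

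The cost is one line moved in each of two lists, with the menstrual history added to each, one line added to Table 3 and one sentence in each of two sections. Participants may have to arrive somewhat earlier on drug visits so that the laboratory result is back. At Visit 3, testing first also avoids randomising a woman who must then be excluded; Visit 4 has no such gain, because randomisation has already taken place.

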### **0.9% Saline Placebo**

- The drug will be stored in line with manufacturer instructions.
- As the study drug will be blinded to the research investigator, the research nurse will be charged with preparing the study drug.
- A dose of 0.01ml/Kg will be drawn up by the research nurse and labeled with the appropriate code **Treatment A** or **Treatment B**.
- The drug will be drawn up using a 1 or 2 ml syringe depending on the volume needed.
- The weight used will have been recorded prior to drug administration.
- This drug will be administered using a sterile technique to the participant's subcutaneous tissue.
- It will be given 60 minutes prior to the Buffet meal.
- A menstrual history and urinary pregnancy test will be completed on all females of child bearing potential prior to the administration of any drug.

### **3.5 Buffet Meal**

The study will take place at the Clinical Research Centre at St Vincents University Hospital. The study methodology will follow the paradigm for food preference assessment developed and validated by Geiselman *et al* [1].

Subjects will be provided with a Food preference questionnaire prior to the study visit. This will ask patients to hedonically/by preference rate each of approximately 90 common foodstuffs of known macronutrient composition on a 9-point Likert scale with the following anchors: 1 = dislike extremely; 5 = neutral; 9 = like extremely. This assessment will be completed by subjects prior to their screening visit, the data sheet will be collected and evaluated by the research investigator. This food preference questionnaire will categorise the 90 food stuffs into each of the 6 cells highlighted in the table below and in no particular order.

Responses from the questionnaire will be used to select appropriate foodstuffs for use in an 18 item buffet spread, for each given subject, from the stock list of 90 items. The 18 items selected for the buffet spread will comprise high fat and low fat options combined with varying carbohydrate and protein content, as depicted in **Table 1**. We will endeavour to provide each subject with foods to which he/she had an intermediate hedonic response (5 – 7). High fat foods given to an individual subject will be paired with a low fat variation of the same food; eg high and low fat meat options, high and low fat cheese options. Stock list foods are all items which are commercially available and require minimal or no preparation (for example slicing fruit, bread or cheese). All food items will be stored and used according to manufacturer’s instructions.

**Table 1: Macronutrient self-selection paradigm**

	High Simple Sugar	High Complex CHO	Low CHO/High Protein
High Fat	Three foods Fat > 40% Sugar >30%	Three foods Fat >40% Comp Carb >30%	Three foods Fat >40% Protein >13%
Low Fat	Three foods Fat <20% Sugar >30%	Three foods Fat <20% Comp Carb >30%	Three foods Fat <20% Protein >13%

Adapted from Geiselman *et al* [1].

Subjects will be asked to fast from 22:00 the night before the study visit. Subjects may drink water during this period. Volunteers will be asked to abstain from alcohol consumption and strenuous exercise for the preceding 24 hours. Medications may be taken as per usual, but this will be discussed with individual subjects in advance of the study day. Subjects will be asked to come to the CRC at 10:30 on the morning of the assessment. On arrival at the CRF, study documentation and body anthropometry will be completed.

Each subject will have access to their own individual buffet table, in separate rooms, such that subjects cannot observe the selections made by other subjects. Order of foods on the buffet spread will be randomised on each study visit. Containers of known weight of the 12 test foods will be provided to each subject. Subjects will be provided with written and verbal instructions prior to commencing the buffet meal. Volunteers will be instructed that they can now eat their meal and consume as much food as they wish in order to feel “comfortably

full". Patients will be made aware that gut hormone responses will not be optimal if they don't reach a state of being comfortably full, eat the foods they like or if they overeat and feel unwell. Subjects will be reminded that it is important that they understand and follow these instructions, as the blood test for gut hormones will be performed on completion of the meal. They may also eat as much of any particular food type they wish and that it is not a competition. All subjects will be provided with still bottle water to accompany the buffet meal.

Each subject will have access to their own individual buffet table. Subjects will be asked to place any mobile electronic devices that they have brought with them into a sealed container in their room, with all electronic devices switched off. Reading material and media sources in the form of television or radio will be provided. Subjects will be instructed to alert the research team when they have finished eating, or should they experience any problems. After providing these instructions and answering any questions the subject may have, the investigator will then leave the room.

At this point a member of the research team will record the exact quantity of each foodstuff chosen by each subject by determining change in test food container weight.

At each of the 12 month visits, patients eligible for randomisation will receive a subcutaneous injection of either 1µg/kg octreotide(Sandostatin® 100microgram/ml) or 0.01ml/Kg 0.9% saline, in a random sequence. The study meal will be initiated directly after the completion of the baseline blood test on study visits not requiring a subcutaneous injection. Where subjects have received an injection of octreotide or saline, the meal will be initiated one hour after injection to ensure adequate serum concentrations of octreotide have been achieved.

### **3.6 Clinical Nutritional Assessment**

All participants will have an assessment by a trained clinical nutritionist at the end of the first study visit. The session include a 45 minute consultation with all participants. It will include a review of current dietary preferences followed by a standardised dialogue guiding subjects on the principles of healthy eating.

#### **4 Protocol Overview/Study visit and Event Schedule**

Outlined below is a detailed overview of the study protocol. **Table 2** summarises the procedures that will be undertaken at each patient visit while **Table 3** outlines the basic schedule of a typical study visit.

##### **Screening Visit**

1. Informed consent
2. Food preference Questionnaire
3. Screening Questionnaire and Eligibility Assessment

##### **Study Visit 1: Week -4**

1. Anthropometric assessment: Height, weight, BMI and waist circumference
2. Fasting Bloods
3. Buffet Meal
4. Post prandial bloods
5. Clinical Nutrition education session

##### **Study Visit 2: Week 12**

1. Anthropometric Assessment: Height, weight, BMI and waist circumference
2. Fasting Bloods
3. Buffet meal
4. Post Prandial Bloods

##### **Study Visit 3: Week 52**

1. Anthropometric Assessment: Height, weight, BMI and waist circumference
2. Fasting Gut peptide level
3. Randomisation to treatment A or B (Saline or Octreotide)
4. Administration of blinded Study drug prior to buffet meal
5. Buffet meal
6. Post prandial bloods
7. Urinary Pregnancy test

##### **Study Visit 4: Week 52**

1. Anthropometric Assessment: Height, weight, BMI and waist circumference
2. Fasting Gut peptide level

3. Administration of blinded study drug prior to buffet meal(A or B determined by previous randomization)
4. Buffet meal
5. Post prandial bloods
6. Urinary Pregnancy test

### Study Visit 5: Week 102

1. Anthropometric Assessment: Height, weight, BMI and waist circumference
2. Fasting Bloods
3. Buffet meal
4. Post Prandial Bloods
5. Discharge from study/Letter to General Practitioner

	Screening Visit	Visit 1 Week -4	Visit 2 Week 12	Visit 3 Week 52	Visit 4 Week 52	Visit 5 Week 104
Informed Consent	X	X				
Height		X	X	X	X	
Weight		X	X	X	X	
Fat mass		X	X		X	
Blood pressure		X	X	X	X	X
Heart rate		X	X	X	X	X
Medical History		X				X
Fasting Gut Peptides		X	X	X	X	X
Post Prandial Gut Peptides		X	X	X	X	X
Pregnancy test		X	X	X	X	X
Administration of Study Drug				X	X	
Food preference Questionnaire	X					
Buffet meal			X		X	
Clinical Nutrition session		X				
GP letter	X					X

**TABLE 3: General study visit schedule**

Time	Action
10:30 to 12.00	Arrive at CRC Complete paperwork, questionnaires and collection of anthropometric data
10.50	Phlebotomy 1 (fasting pre-meal)
11.00	SC injection of octreotide or saline as randomised at 52 week visit
12.00	Commence ad libitum buffet meal Upon completion of the ad libitum meal
14.00	Phlebotomy 2 at 2 hours post meal initiation
14.15	End of Visit

## **5 Adverse event program**

### **5.1 Subject premature Withdrawal**

If a study volunteer fails to complete the study protocol it will be documented in the individual case report form. The reason for failure to complete the study will be included in the CRF. Study Subjects may be withdrawn for the following reasons

- Adverse Event(s) (AEs)
- Abnormal laboratory value(s)
- Protocol violation
- Subject withdrew consent
- Lost to follow-up
- Death

All patients who withdraw early from the study will have their GP informed in writing that their participation in the study is complete. In the event of adverse event, GP's will be informed and arrangements will be made for subjects who have a requirement for ongoing medical follow-up as a consequence of an adverse event.

### **5.2 Adverse Events (In accordance with the ICH)**

An adverse event (AE) is defined as “any untoward medical occurrence in a patient or clinical investigation subject administered a pharmaceutical product and which does not necessarily have to have a causal relationship with this treatment”. The principal investigator (PI) will be informed of any adverse events affecting participants within 24 hours of the research investigator becoming aware of them. The suitability of the participant to continue with the study will be determined by the PI. All adverse events will be recorded in the CRF and the adverse events log contained within the site file. A data safety monitoring committee will be established consisting of senior physicians. All events will be reported within 7 working days and decisions to progress or stop the study will be made in conjunction with the Ethics committee.

### **5.3 Serious Adverse Events**

A serious adverse event (SAE) or reaction is defined as any untoward medical occurrence that:

- results in death
- is life-threatening
- requires inpatient hospitalisation or prolongation of existing hospitalisation
- results in persistent or significant disability/incapacity, or
- is a congenital anomaly/birth defect.

The term "life-threatening" in the definition of "serious" refers to an event in which the patient was at risk of death at the time of the event; it does not refer to an event which hypothetically might have caused death if it were more severe. The principal investigator (PI) will be informed of any adverse events affecting participants within 24 hours of the research investigator becoming aware of them. The suitability of the participant to continue with the study will be determined by the PI. All adverse events will be recorded in the CRF and the adverse events log contained within the site file. A data safety monitoring committee will be established consisting of senior physicians. All events will be reported within 7 working days and decisions to progress or stop the study will be made in conjunction with the Ethics committee.

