### ***11.2 Premature termination of the study***

The principal investigator reserves the right to terminate the study at any time. Adequate consideration must be given to the protection of all study volunteers on termination of the investigation. Subjects will be informed in writing immediately and appropriate follow-up is assured.

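### Serious adverse events have no reporting clock of their own: section 5.3 repeats section 5.2, so oversight bodies may wait 7 working days even for a death

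*Combined protocol and SAP*

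**What the plan says.** Section 5.3 gives serious events their own definition, covering among others deaths and life-threatening events. The handling text that follows is the same as in section 5.2:

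- Notice to the PI: the PI "will be informed of any adverse events affecting participants within 24 hours of the research investigator becoming aware of them".
- The affected participant: "The suitability of the participant to continue with the study will be determined by the PI".
- Oversight: "A data safety monitoring committee will be established consisting of senior physicians". No reporting time to this committee is given.
- Reporting and stopping: "All events will be reported within 7 working days and decisions to progress or stop the study will be made" jointly with the Ethics committee. Section 5.2 has the identical sentence, beginning "All events will be reported within 7 working days".

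Section 11.2 adds a separate power: "The principal investigator reserves the right to terminate the study at any time".

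On dosing, section 4 places the first blinded injection at Visit 3, labelled Week 52, and the second at the visit headed "Study Visit 4: Week 52". Table 2 gives both visits the same week. Section 3.3 says only that the opposite treatment is given at the next study visit.

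**The concern.** A separate definition of a serious event is useful only if something follows from it. Here nothing does: a death and a mild symptom follow the same steps to the same deadlines. The one fast step, notice to the PI, applies to every event. The slower step feeds the decision to continue or stop the study, which sections 5.2 and 5.3 make a joint matter with the Ethics committee. That committee cannot contribute to a decision about an event it has not yet heard of.

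What is at stake is independent review. Phase two gives blinded subcutaneous injections to participants who reach their one-year visits at different times. While a serious event in one of them waits to be reported, others may be dosed without either committee having seen it. The sentence also does not say who receives the report, so the monitoring committee may or may not be on the same clock.

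**Working it through.** The plan states no figure to reproduce. The check is a comparison of the two sections, followed by calendar arithmetic.

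**1. Does being serious change anything?** Sections 5.2 and 5.3 side by side:

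| Step | 5.2, any event | 5.3, serious event |
|---|---|---|
| PI informed | 24 hours from awareness | 24 hours from awareness |
| Participant's continuation | PI decides | PI decides |
| Record | CRF and log | CRF and log |
| Report | 7 working days | 7 working days |
| Recipient of report | not named | not named |
| Continue or stop the study | with the Ethics committee | with the Ethics committee |

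No row differs.

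**2. How long is 7 working days?** Input: 7 working days (sections 5.2 and 5.3). Assumptions: Monday to Friday are working days, there are no public holidays, and the clock starts the day after the event (the sentence gives no starting point).

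- Event on Monday: Tue 1, Wed 2, Thu 3, Fri 4, Mon 5, Tue 6, Wed 7, so 9 calendar days. Tuesday and Wednesday also give 9.
- Event on Thursday: Fri 1, Mon 2, Tue 3, Wed 4, Thu 5, Fri 6, Mon 7, so 11 calendar days. Friday also gives 11.
- Saturday gives 10 and Sunday gives 9.

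The limit is therefore 9 to 11 calendar days, and longer with public holidays. Against the PI's 1 day, the report may follow 9 − 1 = 8 to 11 − 1 = 10 days later, if both clocks start together.

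**3. How does that compare with the gap between the two injections?** The gap is not stated, so only a range can be shown, for an event on the day of the first injection:

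- Both visits in one calendar week: the gap is at most 4 days (Monday to Friday) or 6 days (seven-day week). Since 9 > 6, the full limit outlasts the gap.
- Visits 14 or more days apart: 11 < 14, so the limit ends before the second injection.

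An event later in the gap leaves less time before the second injection.

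**4. Who may stop the study?** Sections 5.2 and 5.3 make it a decision taken with the Ethics committee. Section 11.2 gives it to the PI without mentioning that committee. The text does not say which governs after a serious event.

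**The case against.** The strongest reply is that the PI is told within 24 hours, decides on the affected participant, and can end the study under section 11.2. This stands. A reader might infer from the 7-day sentence that dosing goes on before anyone able to stop the study has been told. The documents do not support that: the PI is such a person, and acting together with the Ethics committee does not oblige the PI to wait for it. What remains is that independent review may lag. The PI's notice does not replace it, because the protocol itself provides for a monitoring committee and for joint decisions.

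A reader might also infer that the reporting clock is longer than the interval between a participant's two injections. Week 52 may be only a nominal label, and section 3.5 speaks of 12-month visits in the plural. The comparison goes either way depending on an interval that is not given.

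Third, 7 working days is a ceiling and allows same-day reporting. That is true, so late notice is permitted and not certain. A deadline is still judged by what it permits.

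Finally, section 11.1 requires the Ethics committee to be told as soon as possible when the protocol is changed without prior approval to remove an immediate hazard. That duty is triggered by the deviation and not by the serious event, so it does not fill the gap.

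**Conclusion.** The point holds as a should-change. On the face of the text, serious events have no expedited route to either oversight body, and the recipient of the report is unnamed. The possible lag is 9 to 11 calendar days, against 24 hours for the PI, on the assumptions of a five-day working week, no public holidays and use of the full limit.

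Other participants may receive blinded injections during that lag whatever the Visit 3 to Visit 4 interval is. That the lag outlasts one participant's own dosing interval is possible, and follows if both visits fall in the same calendar week, but it is not established.

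It would be tempting to count the injections given within one reporting window. The documents do not support a count: phase two is by invitation, section 3.1.2 excludes some participants from octreotide, the spread of visits over time is not given, and the PI may halt sooner.

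**What to change.** - In section 5.3, replace the copied reporting sentence with a separate expedited clock for serious events. Name the data safety monitoring committee and the Ethics committee as recipients and state when the clock starts. The 24-hour basis already used for the PI is one option.
- In section 5.2, keep 7 working days, limited to non-serious events, and name the recipient.
- Reconcile sections 5.2 and 5.3, where stopping is decided with the Ethics committee, with section 11.2, where the PI may act alone.
- Reconcile the shared Week 52 label of Visits 3 and 4 in section 4 and Table 2, so that the relation between the two visits can be read from the protocol.

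The cost is a few sentences in sections 5 and 11.2, a clarification in section 4 and Table 2, and ethics approval of the amendment as section 11.1 requires. The downside in operation is faster paperwork for a small number of serious events.
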